8.6.6. Safety and Tolerability Statistical Methodology.....	25
9. INTERIM ANALYSES	25
10. SIGNIFICANT CHANGES FROM THE PROTOCOL-SPECIFIED ANALYSES	26
11. REFERENCES	26
12. APPENDICES	27

LIST OF ABBREVIATIONS

Abbreviations pertain to the statistical analysis plan (SAP) only (not the tables, figures, and listings [TFLs]).

ADaM	analysis data model
AE	adverse event
Ae_{t1-t2}	amount of the dose administered recovered in urine over the time interval t1 to t2
ANOVA	analysis of variance
AUC_{last}	the area under the plasma concentration-time curve, from time 0 to the last measurable non-zero concentration
AUC_{0-inf}	the area under the plasma concentration-time curve from time 0 extrapolated to infinity
AUC_{τ}	area under the plasma concentration-time curve during a dosing interval hours postdose
$\%AUC_{extrap}$	percentage of AUC_{0-inf} that is due to extrapolation from the last quantifiable concentration to infinity
$\%AUC_{\tau, extrap}$	percentage of AUC_{τ} that is due to extrapolation from the last quantifiable concentration to the end of the dosing interval
BLQ	below the limit of quantification
CDISC	Clinical Data Interchange Standards Consortium
CI	confidence interval
CL/F	apparent clearance following an extravascular dose
CL_R	renal clearance
C_{max}	maximum observed concentration
CSR	clinical study report
C_{trough}	plasma concentration at the end of the dosing interval
CV	coefficient of variation
DMID	Division of Microbiology and Infectious Diseases
ECG	electrocardiogram
EOS	end of study
FDA	Food and Drug Administration
FE	food-effect
Fe_{t1-t2}	percentage of the dose administered recovered in urine over the time interval t1 to t2
FIH	first-in-human
GLSM	geometric least squares mean
ICH	International Council for/Conference on Harmonisation of Technical Requirements for Registration of Pharmaceuticals for Human Use
ln	natural log
LSM	least squares mean

MAD	multiple ascending dose
MedDRA	Medical Dictionary for Regulatory Activities
MR _{AUC}	EIDD-1931:EIDD-2801 ratio based on AUC _{0-inf}
MR _{Cmax}	EIDD-1931:EIDD-2801 ratio based on C _{max}
MW	molecular weight
PBMC	peripheral blood mononuclear cells
PE	physical examination
█	█
PK	pharmacokinetic(s)
QTc	QT interval corrected for heart rate
QTcF	QT interval corrected for heart rate using Fridericia's formula
RA _{AUCτ}	observed accumulation ratio based on AUC _τ
RA _{Cmax}	observed accumulation ratio based on C _{max}
SAD	single ascending dose
SAP	statistical analysis plan
TEAE	treatment-emergent adverse event
TFL	table, figure, and listing
t _{last}	time of the last quantifiable concentration
t _{max}	time of the maximum observed concentration
t _{1/2}	apparent terminal elimination half-life
V _z /F	apparent volume of distribution during the terminal phase following and extravascular dose
WHODrug	World Health Organization Drug Dictionary
λ _z	apparent terminal elimination rate constant

1. INTRODUCTION

This SAP has been developed after review of the clinical study protocols (Final Version 5.1 (United Kingdom) dated 11 June 2020 and Final Version 5.2 (United States) dated 11 June 2020) and electronic case report form.

This SAP describes the planned analysis of the pharmacokinetic (PK) and safety and tolerability data from this study. A detailed description of the planned TFLs to be presented in the clinical study report (CSR) is provided in the accompanying TFL shells document.

In general, the analyses are based on information from the protocol, unless they have been modified by agreement with Ridgeback Biotherapeutics. A limited amount of information about this study (eg, objectives, study design) is given to help the reader's interpretation. This SAP must be finalized prior to the lock of the clinical database for this study. When the SAP and TFL shells are approved, they will serve as the template for this study's CSR.

This SAP supersedes any statistical considerations identified in the protocol; where considerations are substantially different, they will be so identified. If additional analyses are required to supplement the planned analyses described in this SAP, they may be performed and will be identified accordingly in the CSR. Any substantial deviations from this SAP will be agreed with Ridgeback Biotherapeutics and identified in the CSR.

This SAP is written with consideration of the recommendations outlined in the International Conference on Harmonisation (ICH) E9 guideline *Statistical Principles for Clinical Trials* and ICH E3 guideline *Structure and Content of Clinical Study Reports*.^{1,2}

The document history is presented in [Appendix 1](#).

2. STUDY OBJECTIVES

2.1. Primary Objectives

The primary objective of Part 1 of the study is to determine the safety and tolerability of single ascending doses of EIDD-2801.

The primary objective of Part 2 of the study is to assess the effect of food on the PK on EIDD-2801 and EIDD-1931 following a single oral dose.

The primary objective of Part 3 of the study is to determine the safety and tolerability of multiple ascending doses of EIDD-2801.

2.2. Secondary Objectives

The secondary objectives of Part 1 and Part 3 of the study is to define the PK of EIDD-2801 and EIDD-1931 in plasma and urine following single and multiple doses administered to healthy volunteers.

The secondary objective of Part 2 of the study is to determine the safety and tolerability of single doses of EIDD-2801.

2.3. Exploratory Objectives

The exploratory objectives of Part 1 and of Part 3 are to collect data to assess the relationship between EIDD-2801/EIDD-1931 concentrations and QT interval corrected for heart rate (QTc).

3. STUDY ENDPOINTS

3.1. Primary Endpoints

The primary endpoints for Parts 1 and 3 of the study are results of safety evaluations including safety laboratory assessments, physical examinations (PEs), electrocardiograms (ECGs), vital signs, and adverse events (AEs).

The primary endpoints for Part 2 of the study are plasma PK parameters including C_{max} , t_{max} , $t_{1/2}$, CL/F, λ_z , Vz/F, AUC_{0-inf} and AUC_{last} as appropriate.

3.2. Secondary Endpoints

The secondary endpoints are as follows:

- Single-dose plasma PK parameters, including C_{max} , t_{max} , $t_{1/2}$, CL/F, λ_z , Vz/F, AUC_{0-inf} and AUC_{last} as appropriate (Part 1)
- Multiple-dose plasma PK parameters, including C_{trough} , C_{max} , t_{max} , $t_{1/2}$, CL/F, λ_z , Vz/F, AUC_τ, AUC_{0-inf} (Day 1 dose only), RA_{AUCτ} and RA_{C_{max}}, as appropriate (Part 3)
- Urinary excretion of EIDD-2801 and EIDD-1931 following single- and multiple-dose administration (Parts 1 and 3).
- Results of safety evaluations including safety laboratory assessments, PEs, ECGs, vital signs, and AEs (Part 2).

4. STUDY DESIGN

4.1. Overview

EIDD-2801-1001 is a Phase 1, randomized, double-blind, placebo-controlled, first in human (FIH), single ascending dose (SAD), and multiple ascending dose (MAD) study of the safety, tolerability and PK of EIDD-2801 and EIDD-1931 following oral administration of single and multiple doses of EIDD-2801 to healthy volunteers. In addition, for a minimum of one cohort, the effect of food on the single-dose EIDD-2801 and EIDD-1931 PK parameters will be assessed in subjects taking open-label EIDD-2801. The overall objective of the study is to identify a starting dose for future safety and therapeutic intervention trials.

The study is composed of 3 parts; Part 1 is the SAD study, Part 2 is the FE cohort study, and Part 3 is the MAD study.

This study will be conducted at 1 site in the United Kingdom and up to 3 sites in the United States.

4.1.1. Part 1 (Single Ascending Dose)

A single oral dose of EIDD-2801 or Placebo will be administered to subjects. Subjects will be randomized in a 3:1 ratio to receive either EIDD-2801 or Placebo.

Following dosing on Day 1, subjects will remain in the clinic through completion of study assessments on Day 4, returning to the clinic on Day 9 for study assessments, and Day 15 for the end of study (EOS) visit.

The first cohort will be divided into 2 groups. The first group, a sentinel group, will include 2 subjects. On Day 1, one subject in the sentinel group will be administered Placebo and one will be administered EIDD-2801. Analysis of the safety results for the sentinel group will be reviewed 24 hours postdose. If no halting criteria have been met, the remainder of the subjects in Cohort 1 (the second group) will be dosed. There will be no sentinel groups for the remaining cohorts.

After completion of each dosing cohort, safety and tolerability data will be reviewed to determine if any of the halting rules have been met. If not, then the subsequent cohort may be dosed following review of the 72-hour safety data. As PK data become available, these data may be used for dose-escalation decisions.

The proposed dose-escalation scheme is shown in

Figure 1, however, planned dose escalations will be determined based on ongoing review of the safety, tolerability, and available PK data. The starting dose in the first SAD cohort will be 50 mg. Dose levels will not increase by more than 3-fold for predicted nonpharmacologically active dose levels and by 2-fold for predicted pharmacologically active dose levels. The highest total daily dose to be studied under this protocol will not exceed 1600 mg.

Three cohorts are initially planned for Part 1; however, up to an additional 7 cohorts may be enrolled.

4.1.2. Part 2 (Food-Effect)

Two single oral doses of EIDD-2801 will be administered to subjects, in an open-label manner. The dose for the Part 2/food-effect cohort is planned to be 100 mg but may be adjusted based on safety, tolerability, and/or PK data from Part 1. The dose assessed in the Part 2 cohort will have been given previously to subjects in a Part 1 cohort successfully (i.e., no halting rules were met following dosing).

Subjects will be randomized to a treatment sequence; i.e., to receive drug in the fed then fasted state (Sequence 1) versus fasted then fed state (Sequence 2);

Figure 1). Half of the subjects in the cohort will be randomized to Sequence 1 and the other half will be randomized to Sequence 2.

Following dosing on Day 1, subjects will remain in the clinic through completion of study assessments on Day 4, returning to the clinic on Day 9 for study assessments, and Day 14 to begin the second dosing sequence on Day 15. Subjects will then be discharged from the clinic on Day 18, returning to the clinic on Day 23 for study assessments, and Day 30 for the EOS visit. There will be a 14-day (minimum) washout period between doses.

One cohort of 10 subjects is planned for Part 2. However, if PK results obtained are equivocal, additional subjects may be enrolled into the Part 2/food-effect cohort at the previously tested dose or an additional Part 2/food-effect cohort may be added at a different dose.

4.1.3. Part 3 (Multiple Ascending Dose)

Subjects in Part 3 will be randomized in a 3:1 ratio to receive either EIDD-2801 or Placebo. Twice-daily dosing will be administered to subjects on Day 1 through Day 5, inclusive, and a final dose will be administered on the morning of Day 6 for collection of steady-state PK samples during waking hours. Depending on ongoing review of the safety, tolerability, and PK data, the number of days of dosing may be reduced and the dosing frequency may be changed; the dosing frequency will be no less than once-daily or no greater than three-times daily.

The proposed dose-escalation scheme is shown in

Figure 1. The total daily dose will not exceed a dose shown to be safe and well-tolerated in Part 1. Doses in Part 3 may be administered in the fed state, following review of the PK data obtained from Part 2. Part 3 may run in parallel with Part 1, providing that the total daily dose to be administered does not exceed a dose already shown to be safe and well-tolerated in Part 1.

[figure not shown]
Subjects will remain domiciled at the site during the dosing period and until Day 9, returning to the clinic on Day 14 for completion of study assessments, and Day 20 for the EOS visit. If the number of days of dosing are reduced, the timepoints for subsequent assessments and the period for which subjects are domiciled at the clinic will similarly be changed (subjects will be domiciled for 3 days post final dose).

Three cohorts are initially planned for Part 3; however, up to an additional 6 cohorts may be enrolled, or the number of cohorts may be reduced if the study objectives are met. Dose levels in Part 3 may be repeated for collection of peripheral blood mononuclear cells (PBMCs), providing that the dose level did not meet the dose-escalation halting criteria.

[figure not shown]
Additional parts may be added to this study, including a SAD part in elderly healthy subjects and a study of the safety, tolerability, and PK in Japanese subjects. These additional parts may be added via a protocol amendment.

Figure 1: Study Design

[figure not shown]
PART 1: SAD Cohorts

PART 2: Food Effect (FE) Cohort

PART 3: MAD Cohorts**

Abbreviations:

FE: food effect

SAD: single ascending dose

MAD: multiple ascending dose

** Part 3 may run in parallel with Part 1, providing that the total daily dose to be administered does not exceed a dose already shown to be safe and well tolerated in Part 1

***The total daily dose in Part 3 will not exceed a dose shown to be safe and well-tolerated in Part 1

5. SAMPLE SIZE JUSTIFICATION

No formal sample size calculation was conducted. The sample size of 8 per cohort (6 active: 2 Placebo) for the SAD and MAD cohorts is considered adequate for a Phase 1 FIH

study. The sample size of 10 subjects (all administered EIDD-2801) is in accordance with Food and Drug Administration (FDA) guidelines for sample size in food-effect studies.

6. STUDY TREATMENTS

All treatments described are the planned treatments. The TFLs will reflect the actual treatments received, and dose levels will be displayed in increasing order where applicable. Screen failure subjects will have treatment ‘Screen Failure’ presented in all applicable listings.

6.1. Part 1

The study treatment names, abbreviations, and ordering to be used in the TFLs are presented in [Table 1](#).

Table 1: Presentation of Study Treatments in TFLs

Study Treatment	Order in TFLs
Placebo (fasted)	1
50 mg EIDD-2801 [REDACTED] (fasted)	2
100 mg EIDD-2801 [REDACTED] (fasted)	3
200 mg EIDD-2801 [REDACTED] (fasted)	4
400 mg EIDD-2801 [REDACTED] (fasted)	5
600 mg EIDD-2801 [REDACTED] (fasted)	6
800 mg EIDD-2801 [REDACTED] (fasted)	7
XXX mg EIDD-2801 [REDACTED] (fasted)	8

Additional treatment labels may be added in the same format if additional cohorts are required. Amend the formulation as required as changes may occur throughout the study. All Placebo groups will be pooled [REDACTED] for summaries but in the listings the formulation will be indicated in the treatment label as ‘Placebo [REDACTED] (fasted)’ or ‘Placebo [REDACTED] (fasted)’.

As the capsule formulation is expected to be utilized for the latter cohorts, the [REDACTED] EIDD-2801 treatment groups will be summarized after the [REDACTED] EIDD-2801 treatment groups.

6.2. Part 2

The study treatment names, abbreviations, and ordering to be used in the TFLs are presented in [Table 2](#).

Table 2: Presentation of Study Treatments in TFLs

Study Treatment	Order in TFLs
200 mg EIDD-2801 [REDACTED] (fasted)	1
200 mg EIDD-2801 [REDACTED] (fed)	2

Additional treatment labels may be added in the same format if additional cohorts are required. Amend the formulation as required as changes may occur throughout the study.

The study treatment sequence names, abbreviations, and ordering to be used in the TFLs are presented in [Table 3](#).

Table 3: Presentation of Study Treatment Sequences in TFLs

Study Treatment Sequence	Abbreviation	Order in TFLs
200 mg EIDD-2801 ██████ (fed) / 200 mg EIDD-2801 ██████ (fasted)	200 mg EIDD-2801 ██████ (fed/fast)	1
200 mg EIDD-2801 ██████ (fasted) / 200 mg EIDD-2801 ██████ (fed)	200 mg EIDD-2801 ██████ (fasted/fed)	2

Additional treatment sequences may be added in the same format if an additional cohort at a different dose level is required. Amend the formulation as required as changes may occur throughout the study.

6.3. Part 3

The study treatment names, abbreviations, and ordering to be used in the TFLs are presented in [Table 4](#).

Table 4: Presentation of Study Treatments in TFLs

Study Treatment	Order in TFLs
Placebo ██████ BID (fasted)	1
50 mg EIDD-2801 ██████ BID (fasted)	2
100 mg EIDD-2801 ██████ BID (fasted)	3
200 mg EIDD-2801 ██████ BID (fasted)	4
300 mg EIDD-2801 ██████ BID (fasted)	5
400 mg EIDD-2801 ██████ BID (fasted)	6
XX mg EIDD-2801 ██████ BID (fasted)	7

Fasted in the treatment labels above indicates that subjects were fasted prior to the morning dose on PK Days 1 and 6. BID indicates twice daily dosing on Days 1 to 5 and single dose on Day 6. Additional treatment labels may be added in the same format if additional cohorts are required. Amend the frequency, formulation and dietary state as required as changes may occur throughout the study.

7. DEFINITIONS OF POPULATIONS

Any protocol deviations, including those related to COVID-19, will be considered prior to database lock for their importance and taken into consideration when assigning subjects to populations.

7.1. All Subjects Population

The all subjects population will include all subjects who signed the informed consent form and had any study assessment recorded in the database per the protocol.

7.2. Safety Population

The safety population will include all subjects who received at least 1 dose of study drug (EIDD-2801 or Placebo).

7.3. Pharmacokinetic Population

The PK population will include all subjects receiving study drug who comply sufficiently with protocol requirements (i.e., no major protocol violations) and for whom a sufficient number of analyzable PK samples (at least 1 quantifiable postdose sample) have been obtained to permit the determination of the PK profile for EIDD-2801/EIDD-1931 and the statistical analysis of the results. Subjects who experience an AE of vomiting before $2 \times$ the median t_{max} of the group may be excluded from the PK population.

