8. STATISTICAL METHODOLOGY

8.1. General

Listings will be provided for all data captured in the database. Listings will include all subjects assigned to the all subjects population and include data up to the point of study completion or discontinuation. Subjects are generally considered to have completed the study if they completed all protocol-specified procedures and assessments for the end-of-treatment visit. Any subject who discontinued the study will be identified accordingly in the listings. Summaries and statistical analyses will include the subjects assigned to the relevant population based on data type.

Data analysis will be performed using the SAS[®] statistical software package Version 9.4 (or higher if upversioned during the study).

Analysis Data Model (ADaM) datasets will be prepared using Clinical Data Interchange Standards Consortium (CDISC) ADaM Version 2.1 (or higher if upversioned during the study) and CDISC ADaM Implementation Guide Version 1.1 (or higher if upversioned during the study). Pinnacle 21 Community Validator Version 2.2.0 (or higher if upversioned during the study) will be utilized to ensure compliance with CDISC standards.

Caution should be used when interpreting results from the statistical analyses conducted in this study because the sample size is not based on power calculations.

Where reference is made to ‘all calculations’, this includes, but is not limited to, summary statistics, statistical analyses, baseline derivation, changes from baseline, percentage changes from baseline, and any parameter derivations.

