In addition, dose normalized parameters will be calculated for AUC_{last} , $AUC_{0-\text{inf}}$, AUC_{τ} and C_{max} , calculated by dividing the parameter by the administered dose in mg. These parameters will follow the same naming convention as the original parameter with the prefix 'D', eg, DC_{max} .

The following parameters will be where possible from the urine concentrations of EIDD-2801 and EIDD-1931:

Parameter	Units ^a	Definition
Ae_{t1-t2}	mg	amount of the dose administered recovered in urine over the time interval t1 to t2 (calculated by interval and cumulatively)
Fe_{t1-t2}	%	percentage of the dose administered recovered in urine over the time interval t1 to t2 (calculated by interval and cumulatively)
CL_R	L/h	renal clearance

^a Units are based on concentration units (provided by bioanalytical lab) and dose units used in the study.

Additional PK parameters may be determined where appropriate.

Pharmacokinetic analysis will, where possible, be carried out using actual blood sampling times postdose. If an actual time is missing, the sample concentration result will be treated as missing unless there is scientific justification to include the result using the nominal time.

Pharmacokinetic parameters will be derived where possible for all subjects. Data from subjects with incomplete profiles (missed blood draws, lost samples, samples unable to be quantified) may be used if PK parameters can be estimated using the remaining data points.

The following molecular weights (MW) will be used in calculations where required

EIDD-2801 329.31 g/mol

EIDD-1931 259.22 g/mol

C_{max} , t_{last} and t_{max} will be obtained directly from the concentration-time profiles. If C_{max} occurs at more than 1 timepoint, t_{max} will be assigned to the first occurrence of C_{max} .

Parent : prodrug ratios will be calculated as follows:

$$MR_{AUC} = (AUC_{0-inf, EIDD-1931}/MW_{EIDD-1931}) / (AUC_{0-inf, EIDD-2801}/MW_{EIDD-2801})$$

$$MR_{C_{max}} = (C_{max, EIDD-1931}/MW_{EIDD-1931}) / (C_{max, EIDD-2801}/MW_{EIDD-2801})$$

AUC_{last} or other common partial area may be used to determine MR_{AUC} if AUC_{0-inf} cannot be reliably calculated for the majority of subjects.

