8.5.3.1. Dose Proportionality

In Part 1 on day 1 a statistical analysis will be conducted to investigate the dose proportionality of the [REDACTED] formulation for PK parameters of EIDD-2801 and EIDD-1931 (AUC_{0-inf} , AUC_{last} , and C_{max}).

A statistical analysis will also be conducted to investigate the dose proportionality of the [REDACTED] formulation on day 1 for PK parameters of EIDD-2801 and EIDD-1931 (AUC_{0-inf} , AUC_{last} , and C_{max}) by combining the day 1 Part 3 data with the Part 1 [REDACTED] cohorts.

In Part 3 on day 6 a statistical analysis will be conducted to investigate the dose proportionality for PK parameters of EIDD-2801 and EIDD-1931 (AUC_{τ} , and C_{max}). The dose proportionality assessments will include dose levels from a common dietary state.

The PK parameters will be analyzed using a power model³ that will have the following form:

$$parameter = intercept \times dose^{slope} + random\ error$$

Using the natural log (ln) transformation,⁴ a power model can be expressed as a linear regression equation:

$$\ln(parameter) = intercept + slope \times \ln(dose) + random\ error$$

For dose proportionality, the slope of the regression line is equal to 1; for dose independence, it is equal to 0.

For each PK parameter separately, a pooled estimate (across all doses) of slope, corresponding 90% confidence interval (CI), and between-subject coefficient of variation (CV) will be calculated. Figures (on the logarithmic scale) containing individual values, power model line (90% CI), and dose proportionality line (defined as the power model line with slope of 1) will be created for each PK parameter; figures (on the semi-logarithmic scale) containing individual values and geometric means will be created for each corresponding PK parameter normalized by dose administered.

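### The vomiting rule can drop a whole subject from the PK population rather than the affected profile, so a valid Day 6 profile in Part 3 can be lost at discretion

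*SAP*

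**What the plan says.** Section 7.3 defines one PK population for all three parts and ends with this rule: "Subjects who experience an AE of vomiting before $2 \times$ the median t_{max} of the group may be excluded from the PK population". Section 8.1 gives membership its force: "Summaries and statistical analyses will include the subjects assigned to the relevant population based on data type".

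The parts differ in how many doses and profiles a subject has:

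- **Part 1** (Section 4.1.1): one dose.
- **Part 2** (Section 4.1.2): "Two single oral doses of EIDD-2801 will be administered to subjects, in an open-label manner", and "There will be a 14-day (minimum) washout period between doses".
- **Part 3** (Section 4.1.3): two doses a day for five days, then one last dose on the sixth morning. The note to Table 4 agrees ("BID indicates twice daily dosing on Days 1 to 5 and single dose on Day 6") and names Days 1 and 6 as the PK days. Section 8.5.3.1 analyses the second of these separately: "In Part 3 on day 6 a statistical analysis will be conducted to investigate the dose proportionality for PK parameters of EIDD-2801 and EIDD-1931".

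Section 8.5.1 states that "Pharmacokinetic parameters will be derived where possible for all subjects", but the exceptions it goes on to discuss are missed, lost or unquantifiable samples. Section 8.5.1.5 requires strong justification for excluding anomalous values. Neither mentions vomiting. Sections 7 and 8.1.1 say that deviations and data issues are weighed before database lock, without giving a criterion for this case.

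**The concern.** A window of twice the median tmax is a single-dose device: it identifies a dose that may not have been fully absorbed. Section 7.3 attaches it to the subject. Where a subject has more than one profile, the rule therefore reaches data that the event did not touch. A subject who vomits soon after a Day 1 dose in Part 3 can be removed from the Day 6 dose-proportionality analysis and steady-state summaries. A subject who vomits in one period of Part 2 can lose the other period, given at least 14 days apart.

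The rule is also loose in three ways:

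- *May* comes with no criterion and no named decision-maker.
- The window depends on an observed median tmax, so it can be applied only once concentrations exist. The SAP does not say that the decision is made without regard to the subject's exposure.
- *The group* names neither analyte nor day. Section 10 reports that EIDD-2801 was not quantifiable in some treatment groups, so its median tmax may not exist there.

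Two analysts could form different PK populations from the same data. These data carry the Part 3 secondary PK endpoints and, to a lesser extent, the Part 2 primary ones.

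**Working it through.** The SAP states no sample-size or precision calculation (Section 5), so there is no figure of its own to reproduce.

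**Step 1. Profiles exposed to the rule.** Part 3 doses per subject: 2 × 5 + 1 = 11, with PK on Days 1 and 6. Part 2: two doses and two profiles. Part 1: one dose and one profile, so excluding the subject and excluding the profile are the same thing.

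**Step 2. Effect on the planned Part 3 inference.** The Day 6 analysis is a regression of ln(parameter) on ln(dose), pooled over doses, with a 90% CI for the slope (Section 8.5.3.1). Its half-width is t(0.95, N−2) × s / √Sxx, where Sxx is the sum of squares of ln(dose) about its mean. For a given residual SD s, the relative widening does not depend on s. Inputs: 6 active subjects per cohort (Section 5); the five doses named in Table 4 (50, 100, 200, 300, 400 mg); and, as the smaller case, an illustrative three doses (50, 100, 200 mg), because Section 4.1.3 initially plans three cohorts. The profiles lost are at the top dose.

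| Doses | Lost | N | Sxx | t | t/√Sxx | Widening |
|---|---|---|---|---|---|---|
| Five | 0 | 30 | 17.128 | 1.701 | 0.411 | – |
| Five | 1 | 29 | 16.310 | 1.703 | 0.422 | 2.6% |
| Five | 2 | 28 | 15.434 | 1.706 | 0.434 | 5.6% |
| Three | 0 | 18 | 5.765 | 1.746 | 0.727 | – |
| Three | 1 | 17 | 5.257 | 1.753 | 0.765 | 5.2% |
| Three | 2 | 16 | 4.684 | 1.761 | 0.814 | 11.9% |

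**Step 3. A single cohort, for comparison.** For one cohort's geometric mean, t(0.95, n−1)/√n is 0.823, 0.953 and 1.177 at n = 6, 5 and 4. The widening is 0.953/0.823 = 1.16 and 1.177/0.823 = 1.43. The SAP does not plan this interval, so these ratios describe only how thin a cohort summary becomes.

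**Step 4. Possible bias.** If the subject lost happened to have the highest exposure of six, the expected log mean of the other five falls by 1.267/5 = 0.253 SD, where 1.267 is the expected maximum of six standard normal values. With SD = √ln(1 + CV²), that is 0.198 at CV 20% and 0.385 at CV 40%. The geometric mean is then multiplied by exp(−0.253 × 0.198) = 0.95 or exp(−0.253 × 0.385) = 0.91, a fall of about 5% or 9%. The CVs are assumed and this is a worst case.

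**Step 5. Part 2.** In units of the within-subject variance, the variance of the fed–fasted contrast is ½(1/n₁ + 1/n₂), where n₁ and n₂ are the numbers of complete subjects per sequence.

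- Ten complete subjects: ½(1/5 + 1/5) = 0.200.
- One subject dropped: ½(1/4 + 1/5) = 0.225.
- That subject's valid period kept in the mixed model of Section 8.5.3.2: 0.2125 to 0.2238 by generalised least squares, for assumed within-subject correlations of 0 to 0.9.

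Keeping the period lowers the variance by 1 − 0.2125/0.225 = 5.6% at most, and by about 0.6% at correlation 0.9. The signed-rank test on tmax needs both periods, so it gains nothing.

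**The case against.** The strongest reply is that *may* cuts both ways. An analyst can keep a subject whose Day 6 profile is plainly unaffected, and since all concentrations and parameters are listed (Section 8.5.3), an exclusion would be visible. That is fair: loss is possible, not prescribed. But visibility afterwards is not a rule, and the only exclusion the wording offers is of the whole subject.

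A second reply is that a window built on median tmax naturally refers to doses that start a profile, so vomiting after a Day 3 dose would not count. That is a reasonable reading, and the text does not settle it. Section 8.6.1 measures AE onset in Part 3 from the last dose; if that means the most recent one, an event after any dose could fall inside the window. The point does not depend on this, because a Day 1 event can remove Day 6 on either reading.

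A third reply is that Part 2 hardly matters for the food-effect contrast, because the affected period is lost either way. The working bears this out.

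A reader might infer more than the documents support:

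- That vomiting concentrates at the higher doses and so distorts the slope. This is plausible, but the SAP gives no vomiting rate and no relation to dose or food.
- That precision falls by 16% to 43%. Those figures belong to a single-cohort interval that is not planned.
- That the Part 2 primary comparison is materially compromised. It is not.

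**Conclusion.** The point holds as a modest defect in the definition of the analysis set, chiefly for Part 3. Section 7.3 permits removal of the subject, Section 8.1 makes membership decisive, and nothing in the SAP limits the removal to the affected profile. The cost to the planned Day 6 slope is a 90% CI about 3% to 5% wider for one lost top-dose profile and about 6% to 12% wider for two. This assumes 6 active subjects per cohort, no other losses, and five or three dose levels. In Part 2 the loss falls mainly on the by-treatment summaries, and the contrast would gain at most about 6% in variance. Part 1 is unaffected.

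Bias cannot be sized from the document: it depends on which subject is removed. The more lasting weakness is that the choice is discretionary and made once concentrations exist. The study has no power calculation and Section 8.1 already urges caution in interpretation, so no formal conclusion is overturned. A profile-level rule is nevertheless simply the better method.

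**What to change.** Rewrite the last sentence of Section 7.3 so that the exclusion acts on the profile:

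- The subject stays in the PK population.
- When vomiting occurs within twice the median tmax for that analyte, treatment and PK day, after the dose that starts a PK profile, exclude only that analyte's profile from summaries and statistical analysis. Exclude with it any ratio that depends on it, such as the accumulation ratios, which need both days.
- Assess vomiting after a dose shortly before Day 6 against a criterion stated in advance, without regard to the subject's exposure values. A blanket ban on exclusion would go too far here, since such an event could affect the Day 6 profile and the SAP gives no half-life to rule that out.
- Document each exclusion, and give a sensitivity analysis that includes the excluded profiles.

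The window should be set per analyte, because the two analytes can differ in tmax. The cost is a short edit to Section 7.3, one profile-level flag in the PK dataset and one sensitivity analysis. Some subjects will contribute one profile only.
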